7.5 Investigational Device Accountability

The site must maintain a device accountability log. Completion of this log will ensure that all investigational devices are properly tracked and accounted for throughout the study from the time they are received by the institution to the time they are returned to the study sponsor or other designated site. Device location, Subject ID assigned, date Subject returned to site (if assigned to Group A subject), controller disinfected, and final disposition (e.g., returned to sponsor, garments discarded) of all pneumatic compression devices and garments will be documented. The sponsor must also maintain device accountability documenting all shipments and returns of investigational devices by serial number, date, and person completing the log. Storage locations for the investigational devices and garments will be secure (i.e., locked and away from other devices) with access restricted only to investigators and authorized research personnel.

Sanitation Procedure:

At the conclusion of each treatment session the clinic will disinfect the controller and store the subject's garments which must be clearly labeled with subject identification information until the next treatment to ensure that the garments are not used on other study subjects. Group A will be taking a controller and their FT garments home for the weekend. Upon return that site must disinfect the controller before using in clinic. The subject garments should be stored like all other subject assigned study garments. The garment(s) **CANNOT** be reused on multiple subjects and should be appropriately discarded upon study completion.

8.0 Statistical Plan

8.1 Study Design: This study is a prospective, randomised, proof of principle clinical trial to determine the optimal treatment duration and frequency between three options for treating lower extremity lymphoedema with the Flexitouch® system (FT). Optimal treatment duration will be determined by a nested series of physiologic and clinical changes induced by FT treatment within three key outcomes categories: (a) fluid dynamics (as assessed by bioimpedance, perometry, and local tissue water assessments); (b) tissue characteristics/fibrosis (by ultrasound and tonometry measurements); and (c) patient-reported outcomes (quantified by symptom assessment tools, treatment assessments, treatment adherence, and subject interview.) Patient demographics will be summarized and compared between the randomised groups.

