Flexitouch® system (Tactile Systems Technology, Inc., Minneapolis, MN, USA): The FT is a programmable, segmental, gradient pneumatic compression device which has been cleared by the FDA for market in the US (K013061, K120972), by Health Canada for market in Canada (88415) and by European Union for market in Europe (CE 0459) for the treatment of lymphoedema, primary lymphoedema, post mastectomy oedema, oedema following trauma and sports injuries, post immobilization oedema, and venous insufficiencies. Additionally, the device has been cleared to market in the US by the FDA (K062818) for reducing wound healing time as well as the treatment and assistance in healing stasis dermatitis, venous stasis ulcers, arterial ulcers and diabetic leg ulcers (Appendix A).

4.0 Study Objectives: The study objectives have been selected in this proof of principle study in order to determine if there is a difference in treatment effect across the 3 study groups when treating lower extremity lymphoedema using the Flexitouch® system.

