5.0 Study Design

5.1 Overview of Study Design: This study is a 3 arm, prospective, randomised, proof of principle clinical trial to determine the optimal treatment duration for achieving a measurable physiologic effect on lower extremity lymphoedema with the Flexitouch® system (FT) as determined by bioimpedance, perometry, tonometry, ultrasound, local tissue water assessment, symptom burden and subject interview.. Each intervention arm will include 10 completed subjects for a total of 30 completed subjects.

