Group A: subjects will receive 12 consecutive days of treatment utilizing the following treatment regimen. The first 5 days will be in clinic (Monday through Friday) followed by self administered at home treatment for 2 days (Saturday and Sunday). The last 5 days of treatment will be in clinic ending the treatment phase on day 12 (Monday through Friday).

- One lower extremity treatment per day using program L1 with the pressure set to "normal" applying the full garment set.

Groups B & C subjects will receive 5 consecutive days of treatment in clinic (Monday through Friday) utilizing the following treatment regimens.

- Group B: Two lower extremity treatments per day (am and pm) using program L1 with pressure set to "normal" applying the full garment set.
- Group C: Two consecutive treatments 2 times a day (am and pm) using program L1 with pressure set to "normal" applying the full garment set.

In the case of bilateral lymphoedema, the leg with the largest volume will be considered the study leg. The contralateral (non study) leg will be treated in the same manner that it was being treated prior to entering the study. Limb volume measures for both legs will be collected.

At the screening visit, each subject's compression garment(s) will be assessed for clinical adequacy (Class: $\geq 20\text{mmHg}$; Age: 3 months or less) by the Principal Investigator. Subjects will be instructed to wear the compression garment(s) every day during wakeful time. Garments may be removed while bathing and overnight. The clinician will remove the subject's compression garment during device treatment. This treatment regimen is consistent with standard home care compression garment(s) treatment.

7.2 Subject Data Requirements: The following data will be collected from all subjects:

Key: B = Before Treatment A = After Treatment D = During Visit	Screening	Baseline/ Initial Treatment (D1)	Treatment (≠ D1, 5 & 12)	Day 5(All Groups) and Day 12 (Group A)
Medical History	D			
Bio Impedance		B A	B A	B A
Perometer		B A	B A	B A
Duplex U/S	B			
Interface Pressure		B	B	B
Ultrasound		B		A
Tonometry		BA	BA	BA
Moisture Meter D		B A*	B A*	B A*
Subject Interview				D
MyMOP		D		D
Activity Level		D	D	D
BMI		D	D	D
Adverse effects		A	A	A
Compliance		D	D	D

*Group C: Will have moisture meter done before the first treatment session, after the first treatment session, and then after the final treatment session of the day = 3 times total during treatment visits.

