8.2 Efficacy Analysis

Analysis will be undertaken for the following groups:

Group A: One lower extremity treatment per day using program L1 with the pressure set to “normal” utilizing the full garment set over 12 days. Total number of treatment hours=12.

Group B: Two lower extremity treatments per day (am and pm) using program L1 with pressure set to “normal” utilizing the full garment set over 5 days. Total number of treatment hours=10.

Group C: Two consecutive treatments 2 times a day (am and pm) using program L1 with pressure set to “normal” utilizing the full garment set over 5 days. Total number of treatment hours=20.

This study is planned to have a maximum of 30 completed subjects, 10 in each group with unilateral or bilateral primary or secondary leg lymphoedema. Each subject will receive the FT as per the groups described above. This small sample size will not offer a powered statistical analysis for any single outcome measurement, but is designed to estimate treatment effects for each proposed endpoint for evaluation in a subsequent clinical trial. This study is designed to determine both which measurement endpoints are most sensitive to the variable dosing protocols and to determine which endpoint should be defined as the primary end-point in a larger investigation of compression “dosage”. The study will be used to find the effect size for comparisons between the doses and from this to estimate a suitable sample size for a definitive study.

Subjects with missing data for the study outcomes will be included in the intention to treat analysis. However, the study will continue to enroll until there are 10 subjects in each arm that complete all study visits. After 30 patients have been randomised, those patients who fail to complete all treatment visits will be replaced until all data are available for 10 subjects in each study group. Data from the subjects who fail to complete will be used to determine the adherence to therapy in each randomised group.

Study analysis will be conducted for “within day” change as well as “between day” change. “Within day” change is defined as a comparison of pre-treatment measures against post-treatment measures following the last treatment of the day. “Between day” change is defined as a comparison of pre-treatment outcomes on treatment day 1 compared to post-treatment outcome measures on the final treatment day (day 12 for group A, day 5 for groups B and C).

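### The stated aim of determining the optimal treatment duration and frequency goes beyond what three bundled regimens with 10 completers each can support

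*Combined protocol and SAP*

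**What the plan says.** The aim is stated in three ways.

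- Section 4.0 asks the trial to "determine if there is a difference in treatment effect across the 3 study groups".
- Section 5.1 says it is "to determine the optimal treatment duration for achieving a measurable physiologic effect on lower extremity lymphoedema". Frequency is not mentioned.
- Section 8.1 says it is "to determine the optimal treatment duration and frequency between three options for treating lower extremity lymphoedema". It bases the optimum on a nested series of changes in three categories: fluid, tissue and patient-reported outcomes.

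Section 8.2 then limits what can be concluded: "This small sample size will not offer a powered statistical analysis for any single outcome measurement". It says the results will supply effect estimates, a choice of primary endpoint and a sample size for a definitive study.

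The regimens are in 7.1 and 8.2. Group A "subjects will receive 12 consecutive days of treatment utilizing the following treatment regimen", one treatment a day, with the weekend treatments self-administered at home; for this group 8.2 gives "Total number of treatment hours=12". The twice-daily arms run for 5 days: "Group B: Two lower extremity treatments per day (am and pm) using program L1" (10 h in total), and "Group C: Two consecutive treatments 2 times a day (am and pm") (20 h in total).

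Section 8.2 ranks the categories: fluid first, then tissue, then patient-reported outcomes. Section 8.2.1 expects bioimpedance to be the most relevant measure. Section 5.3 defines complication endpoints, which are not in any of the three categories.

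**The concern.** Calling a duration or a frequency optimal needs two things: a contrast in which that component varies while the others stay fixed, and a stated way to get from the results to a choice. A regimen has three components here (sessions per day, session length, days of treatment), and three arms vary them in bundles. A report that followed 8.1 literally could attribute to duration or frequency a difference that belongs to a whole regimen or to total hours. It could also do so without setting complications beside the effect, although the arms differ up to twofold in total hours. Sections 4.0 and 8.2 ask for less, so the protocol gives the authors of the report two incompatible aims.

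**Working it through.** **1. Reproduce the hour totals.** No treatment length is given in the sections that define the regimens. The totals in 8.2 imply 1 h per treatment. Total hours = sessions per day × hours per session × days.

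| Arm | Sessions/day | h/session | Days | Total h | Stated in 8.2 | h by day 5 |
|---|---|---|---|---|---|---|
| A | 1 | 1 | 12 | 1×1×12 = 12 | 12 | 5 |
| B | 2 | 1 | 5 | 2×1×5 = 10 | 10 | 10 |
| C | 2 | 2 | 5 | 2×2×5 = 20 | 20 | 20 |

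All three totals agree exactly.

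**2. Compare the completed regimens in pairs.**

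| Pair | Components that differ | Total hours |
|---|---|---|
| A vs B | sessions/day and days (and home weekend treatment in A) | 12 vs 10 |
| A vs C | sessions/day, session length and days (and home weekend treatment in A) | 12 vs 20 |
| B vs C | session length only | 10 vs 20 |

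B versus C is the only pair that varies session length with the other two components fixed, and even there longer sessions cannot be separated from doubled hours. Sessions per day and number of days always change together. The final comparison in 8.2 also sets day 12 in A against day 5 in B and C. If duration means course length rather than session length, every contrast that varies it also varies frequency.

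**3. Look for a rule that leads to a regimen.** The category ranking (8.2) and the priority of bioimpedance (8.2.1) say which results matter most. They give no threshold or contrast that would select an arm.

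**4. Precision.** The plan states no power calculation, SD or alpha. Assume one value per subject, a common SD, 10 per arm, no covariates and 95% intervals. The standard error of a pairwise difference is √(2/10) = 0.447 SD.

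- SD from the two arms compared (18 df): 2.101 × 0.447 = 0.94 SD.
- SD pooled over three arms (27 df): 2.052 × 0.447 = 0.92 SD.

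**5. Illustration of choosing an arm.** Suppose the arm with the best observed mean were chosen. This rule is assumed and is not in the plan. Each arm mean has standard error 1/√10 = 0.316 SD. In a simulation of 400,000 trials with one arm truly better than two equal arms, the better arm was chosen as follows.

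| Assumed true advantage | Correct choice |
|---|---|
| 0.3 SD | 62% |
| 0.5 SD | 78% |
| 0.8 SD | 93% |

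With no true difference each arm is chosen one time in three. Section 8.2.1 says the size of the bioimpedance effect is unknown, so the documents do not indicate which row applies.

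**The case against.** The best reply is that this is a declared proof-of-principle pilot. Section 4.0 asks only about differences, 8.2 disclaims power, and 8.1 speaks of three options, which can be read as a choice among whole regimens. On that reading an arm with longer sessions once a day is not needed. The written analysis is a set of repeated-measures mixed models, which may be more precise than the one-value-per-subject figures above. Most of this stands, and it limits the harm. It does not reconcile 5.1 and 8.1 with 4.0 and 8.2.

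A second reply is that 8.2.1 models change at each visit, so A and B can be compared at day 5, before the home weekend. That contrast does hold session length and days fixed. But hours by then are 5 versus 10, so frequency is again tied to doubled dose, and the plan does not assign the contrast to the frequency question.

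A reader might also infer more than the documents support:

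- *That the trial will name the arm with the best mean.* No section says so.
- *That only B and C differ in session length.* A and C differ too, but together with everything else.
- *That safety plays no part.* Adherence and treatment assessments belong to the third category, 8.3 reviews withdrawals and their reasons, and 12.2 allows termination for severe events in any arm. Only the formal complication endpoints are left out.
- *That the next trial will inherit a chosen dose.* Section 8.2 carries forward effect sizes, an endpoint and a sample size.

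**Conclusion.** The concern holds as a mismatch between the stated aim and the design. The claim of an optimal duration (5.1) or an optimal duration and frequency (8.1) is not supported: no pair of completed regimens isolates frequency or course length, and the one pair that isolates session length also doubles total hours. The absence of a selection rule is missing detail and would not carry the point alone. Together with the confounding and an interval of about ±0.92 to 0.94 SD, it means no arm could properly be called optimal.

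The arm structure follows from the documents, given 1 h per treatment as implied by 8.2. The interval rests on unadjusted single values. The selection percentages rest on an assumed rule and assumed effects, and at 0.8 SD the choice would usually be right. The planned models and effect estimates are unaffected; what must change is the conclusion they are said to support.

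**What to change.** In 5.1 and 8.1, replace the aim of determining an optimum with: *estimate differences in effect between three treatment regimens, with 95% confidence intervals*. This agrees with 4.0 and 8.2. Then state that:

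- B versus C, on every planned endpoint with the bioimpedance ECF/ICF change read first, informs longer sessions together with the doubled total hours. Keeping every endpoint preserves the 8.2 aim of learning which measures respond most to dosing.
- Contrasts with A compare whole regimens and do not isolate frequency or course length. If A and B are also compared at day 5, the difference in hours (5 versus 10) is to be reported with the result.
- No regimen will be declared optimal from this study.
- Complications and withdrawals will be tabulated by arm beside the effect estimates.

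The cost is a more modest stated aim and one extra table. Arms, regimens and sample size stay as they are.

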8.2 Efficacy Analysis

Analysis will be undertaken for the following groups:

Group A: One lower extremity treatment per day using program L1 with the pressure set to “normal” utilizing the full garment set over 12 days. Total number of treatment hours=12.

Group B: Two lower extremity treatments per day (am and pm) using program L1 with pressure set to “normal” utilizing the full garment set over 5 days. Total number of treatment hours=10.

Group C: Two consecutive treatments 2 times a day (am and pm) using program L1 with pressure set to “normal” utilizing the full garment set over 5 days. Total number of treatment hours=20.

This study is planned to have a maximum of 30 completed subjects, 10 in each group with unilateral or bilateral primary or secondary leg lymphoedema. Each subject will receive the FT as per the groups described above. This small sample size will not offer a powered statistical analysis for any single outcome measurement, but is designed to estimate treatment effects for each proposed endpoint for evaluation in a subsequent clinical trial. This study is designed to determine both which measurement endpoints are most sensitive to the variable dosing protocols and to determine which endpoint should be defined as the primary end-point in a larger investigation of compression “dosage”. The study will be used to find the effect size for comparisons between the doses and from this to estimate a suitable sample size for a definitive study.

Subjects with missing data for the study outcomes will be included in the intention to treat analysis. However, the study will continue to enroll until there are 10 subjects in each arm that complete all study visits. After 30 patients have been randomised, those patients who fail to complete all treatment visits will be replaced until all data are available for 10 subjects in each study group. Data from the subjects who fail to complete will be used to determine the adherence to therapy in each randomised group.

Study analysis will be conducted for “within day” change as well as “between day” change. “Within day” change is defined as a comparison of pre-treatment measures against post-treatment measures following the last treatment of the day. “Between day” change is defined as a comparison of pre-treatment outcomes on treatment day 1 compared to post-treatment outcome measures on the final treatment day (day 12 for group A, day 5 for groups B and C).

This study will evaluate FT-induced changes in three types of outcome measurements categorized as:

- (a) fluid dynamics (measured via bioimpedance; moisture meter; and perometry);
- (b) subcutaneous tissue density (a presumed surrogate marker of tissue fibrosis measured via tonometry)
- (c) patient reported outcomes addressing symptoms, treatment satisfaction; and treatment adherence (measured via MYMOP; patient survey and adherence diary).

Although this is a pilot study with multiple outcomes, the outcome measurement order as listed above indicates a *pre hoc* identification of the order of significance of the outcome measures (change in fluid dynamics > change in tissue fibrosis > change in patient outcomes) in this short-term dose-finding trial.

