8.2.1 Analysis of Fluid Dynamics/Change

Bioimpedance measurement

It is hypothesized that changes in the intracellular and extracellular fluid ratios as measured by multifrequency bioimpedance will yield the most relevant pilot data indicative of treatment success. At present there is no indication of the magnitude of the effect expected using bioimpedance. However, since this is a comparative study, any difference in ECF/ICF change will be evaluated between the three groups. This will be determined using a linear mixed model with repeated measures.

For the within day measures the change in ECF/ICF will be calculated, and used as the dependent variable. Assigned group and day of visit will be forced into the model to allow for comparisons between groups and changes over time ECF/ICF ratio at baseline, BMI, time of day measurements are taken, activity level (number of hours upright and ambulatory), age, number of hours utilizing compression garment, will be tested for inclusion in the model.

To evaluate the between day outcome the change in ECF/ICF from baseline (pre-treatment) will be calculated for each follow up visit (post-treatment), with assigned group and day of visit forced into the model. Identical confounding variables will be used as for the within day analysis.

Final analysis will examine the change in ECF/ICF ratio from baseline to end of final treatment using the same model as above.

Local Tissue Water

Local Tissue Water (LTW) will be assessed prior to and post-treatment at each visit as for the bioimpedance data. The analysis will therefore be undertaken in a similar way to the bioimpedance data.

Perometry

Perometry will be used to estimate limb volume pre and post treatment. The analysis will therefore be undertaken in an identical way as for the bioimpedance measurements.

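### The final-day model for the fluid outcomes, with day of visit forced in, does not deliver the Group A versus B or C contrast it is meant to estimate, and no time-matched day-5 contrast is specified

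*Combined protocol and SAP*

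**What the plan says.** All references are to the combined protocol and SAP.

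- Section 8.1 gives the aim as "to determine the optimal treatment duration and frequency between three options for treating lower extremity lymphoedema".
- Section 8.2 defines between-day change from day-1 pre-treatment values "compared to post-treatment outcome measures on the final treatment day (day 12 for group A, day 5 for groups B and C"). It also defines a within-day change.
- Section 8.2 gives the use of the results: "The study will be used to find the effect size for comparisons between the doses and from this to estimate a suitable sample size". The sample size meant is that of the later, definitive trial. The section does not tie that step to any one analysis.
- Section 8.2.1, on bioimpedance, specifies the model: "This will be determined using a linear mixed model with repeated measures". For the between-day outcome, change from baseline "will be calculated for each follow up visit (post-treatment"). The model for it is specified "with assigned group and day of visit forced into the model". No group-by-day term is named.
- Section 8.2.1 then adds: "Final analysis will examine the change in ECF/ICF ratio from baseline to end of final treatment using the same model as above".
- Perometry is to be analysed identically. For local tissue water the wording is weaker: "The analysis will therefore be undertaken in a similar way to the bioimpedance data".
- Sections 7.1 and 7.4.10 put Group A in clinic on days 1 to 5 and 8 to 12, and Groups B and C on days 1 to 5. The table in section 7.2 schedules the fluid measures on day 5 in all groups and on day 12 in Group A.

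**The concern.** The final analysis is the natural source of the between-regimen effect. It compares Group A on day 12 with Groups B and C on day 5, yet its model also adjusts for day of visit. In the final-day data no two subjects in different positions on that A versus B/C comparison share a day, so the adjustment removes the comparison it is meant to refine.

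There is a second, separate limit. Section 8.1 names both duration and frequency as aims. A and B are the only pair that differs in sessions per day at equal session length, and they are time-matched only up to day 5. At end of course the difference between them mixes frequency with seven more days of treatment and elapsed time. Day 5 is measured in every arm, but no day-5 between-arm contrast is named for the fluid outcomes.

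No confirmatory test is at risk. What could go wrong is that the effect size passed to the definitive study comes from an ad hoc repair of the model, chosen after the data are seen.

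**Working it through.** **Inputs.** Ten completers per group; 1, 2 and 4 sessions per day in A, B and C; courses of 12, 5 and 5 days (sections 7.1 and 8.2). The plan gives no effect size, SD, correlation, alpha or power, so those below are assumptions.

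**Plan's own figure.** At one hour per session (implied by 12 hours in 12 sessions), total hours are 12×1 = 12, 5×2 = 10 and 5×4 = 20, as section 8.2 states. At day 5 they are 5, 10 and 20, so A and B change order between the two time points.

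**1. One final record per subject, day kept.** The columns are intercept, B, C and day. Day is 12 in A and 5 in B and C, so day = 12 − 7·B − 7·C exactly, and the rank is 3 of 4. Lowering the day coefficient by any k, raising the intercept by 12k and lowering the B and C coefficients by 7k leaves every fitted value unchanged. B−A and C−A are therefore not estimable. C−B is, because both coefficients shift equally. Treating day as categorical gives the same rank. Without day the rank is 3 of 3 and every group contrast is estimable.

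**2. All visits, group plus day, no interaction.** This model can be fitted. To see what it estimates, assume that response is proportional to cumulative hours. On day d the gaps are then B−A = 2d − d = d and C−A = 4d − d = 3d.

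- Day 5: B−A = 5, C−A = 15.
- End of course: B−A = 10 − 12 = −2, C−A = 20 − 12 = 8.
- Categorical day: days 8 to 12 come from A alone, so the group coefficient averages the gaps over the shared days. For days 1 to 5 the mean of d is 3, giving 3 and 9 (60% of the day-5 gaps). If day 1 is not counted as follow-up, the mean over days 2 to 5 is 3.5, giving 3.5 and 10.5 (70%).
- Linear day: A's later visits also enter, through the slope, and the result depends on the covariance structure.

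| Model | Visits from day 1: B−A, C−A | Visits from day 2: B−A, C−A |
|---|---|---|
| Categorical day | 3.0, 9.0 | 3.5, 10.5 |
| Linear day, independence or compound symmetry | 3.9, 9.9 | 4.1, 11.1 |
| Linear day, AR(1) 0.8 | 5.0, 11.0 | 5.2, 12.2 |

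The targets are 5 and 15 (day 5) or −2 and 8 (end of course). One cell, B−A of 5.0, meets a target, and only under that covariance and visit set.

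**3. How the two contrasts are related.** This needs no response curve. B's and C's day-5 records serve in both contrasts, so for complete subjects and unadjusted means:

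(B−A at end of course) = B5 − A12 = (B5 − A5) − (A12 − A5),

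and likewise for C. They differ by exactly Group A's own mean change from day 5 to day 12.

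**4. Size, on assumed effects.** n per arm = 2(1.960 + 0.842)²/d² (two-sided 5%, 80% power, equal SD). With a day-5 effect of 0.5 SD and a further gain in A of 0, 0.1, 0.2 or 0.3 SD, d is 0.5, 0.4, 0.3 or 0.2, and n is 63, 99, 175 or 393.

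**5. Chance alone.** If A does not truly change after day 5, the two estimates still differ, with SD √(2(1−ρ)/10), where ρ is the correlation of A's day-5 and day-12 values. For ρ = 0.5, 0.8 and 0.9 this is 0.32, 0.20 and 0.14 SD units. The correlation of the two contrasts is r = (1+ρ)/2. Taking the larger overstates the effect on average by √(2/10)·√((1−r)/π) = 0.13, 0.08 and 0.06 SD.

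**6. Scale.** The 95% CI half-width of either contrast is t(0.975, 18 df)·√(2/10) = 2.101 × 0.447 = 0.94 SD.

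**The case against.** The best defence is that the plan does point to an answer. The definition in section 8.2 and the final analysis in section 8.2.1 both describe end of course, and no day-5 alternative is offered for the fluid outcomes. A sensible analyst would see that a repeated-measures model cannot apply literally to one record per subject, drop the redundant day term, and obtain a legitimate comparison of whole regimens as randomised. Change at every visit is already to be calculated, so day-5 values will exist. The study is declared unpowered, and choosing the future primary endpoint from its data is one of its aims.

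Much of this stands. A reader might infer that the plan is silent on which contrast it intends. It is not: end of course is the readable default, and only the explicit link to the sample-size step is missing. That link is missing for within-day change too, so the open choice is wider than day 12 against day 5. A reader might also infer that comparing A on day 12 with B and C on day 5 is invalid. It is not, because the regimens differ in length by design.

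What does not fall away is that the model as worded cannot yield that default contrast, and that dropping day still leaves frequency and course length mixed in A versus B. Having day-5 values is also not the same as specifying a day-5 contrast.

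**Conclusion.** The point holds and should be fixed. Followed literally, the final-day model gives no A versus B or A versus C effect, and the all-visit version gives one that in general answers neither question. That part rests on the design alone. C versus B at the final visit is unaffected, since both groups end on day 5. The defect applies to bioimpedance and perometry, and to local tissue water as far as its analysis follows the same model.

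The size is not known from the documents. The range of 63 to 393 per arm rests on an assumed 0.5 SD day-5 effect, assumed further change in A and equal SDs. The model coefficients rest on an assumed linear response. A reader might infer that the A versus B effect will reverse sign between day 5 and end of course. That follows from the assumed curve, not from anything in the plan. The 0.06 to 0.13 SD overstatement applies only if the larger estimate is picked, and it is small beside the 0.94 SD half-width. Imprecision is the larger limit on the effect size carried forward. The unclear model adds to it avoidably.

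**What to change.** In sections 8.2 and 8.2.1:

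1. Fit the end-of-course comparison without the day term, and label it a whole-regimen contrast that includes seven more days for Group A.
2. Add a pre-specified time-matched contrast, day-1 pre-treatment to day-5 post-treatment in all three groups. It can come from a simple comparison of day-5 change or from a mixed model on days 1 to 5 with a group-by-day term.
3. State in advance which analysis (end of course, day 5 or within day) supplies the effect size for the definitive study, and report the end-of-course and day-5 contrasts with confidence intervals.

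The cost is a few sentences. No visit, measurement or subject is added. Before covariates, the simple day-5 comparison uses 3 fixed-effect parameters on 30 records, and the interaction model 3×5 = 15 on 30×5 = 150. The drawbacks are a little more analysis, and that the day-5 contrast reads Group A after 5 of its 12 treatments. It complements the whole-regimen contrast and does not replace it.
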